## Coding systems utilized

The original database uses the following variables which are of interest for the data analysis. In the following list, unless otherwise noted, x represents the moment of measurement (1=baseline, 4=last visit at 90 days after treatment). Note that for Barthel Index and modified Rankin Scale, only scores at visits 2, 3, and 4 (30, 60 and 90 days after baseline, respectively) are available, with no value at baseline.

- RDMNUM = randomization number (unique to each participant)
- 
- Western Aphasia Battery
  - WABAQ\_x = Aphasia Quotient (0-100%)
- NIH Stroke Scale (Score)
  - NIHSST\_x = total score (0-42)
- Barthel Index
  - BIT\_x = total score (0-100)
- Modified Rankin Scale

- MRS\_x = total score (0-6 where 0=no symptom and 6=dead)

AEs and SAEs were stored in a separate database, from which we will retrieve the following information:

- Randomization number
- Whether the AE represents a SAE or not
- Based on the nature of the AE, some will be further classified by a clinician as being of the following nature:
  - Neurological
  - Psychiatric
  - Cardiovascular
  - Renal
  - Hematological
  - Gastrointestinal
  - Metabolic
  - Respiratory
  - Immune-related
  - ENT
  - Ophthalmic

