## Study schedule

### Visit schedule

- Visit 1 - Day 0 - Baseline, 3-5 days post-stroke
  - Demographics
  - Medical history
  - Western Aphasia Battery
  - NIHSS
- Visit 2 - Day 30  $\pm$  3
  - Western Aphasia Battery
  - NIHSS
  - Barthel Index
  - modified Rankin Scale
  - Adverse Events (AE)
  - Severe Adverse Events (SAE)
- Visit 3 - Day 60  $\pm$  3
  - Western Aphasia Battery
  - NIHSS
  - Barthel Index
  - modified Rankin Scale
  - Adverse Events (AE)
  - Severe Adverse Events (SAE)
- Visit 4 - Day 90  $\pm$  3
  - Western Aphasia Battery

- NIHSS
- Barthel Index
- modified Rankin Scale
- Adverse Events (AE)
- Severe Adverse Events (SAE)

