### Efficacy

- Comparison of the National Institutes of Health Stroke Scale (NIHSS) scores between the Cerebrolysin and placebo groups at each time point (30, 60, and 90 days after study inclusion) compared to baseline. The NIHSS is a widely used tool for assessing stroke severity and neurological deficits. Paired-measurement statistical tests will be used to analyze the NIHSS scores for each time point compared to baseline, in each group. Unpaired-measurement statistical tests will be used to determine the differences between efficacy of the treatment between groups, at each time point.
- Comparison of the modified Rankin Scale (mRS) scores between the Cerebrolysin and placebo groups at each follow-up time point (30, 60, and 90 days after study inclusion), as well as comparisons between the scores at 3rd and 4th visits compared to 2nd visit. The mRS is a commonly used measure of global disability and functional outcome in stroke patients.
- Comparison of the Barthel Index (BI) scores between the Cerebrolysin and placebo groups at each follow-up time point (30, 60, and 90 days after study inclusion), as well as comparisons between the scores at 3rd and 4th visits compared to 2nd visit. The BI is a measure of functional independence in activities of daily living.

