## Statistical analysis

For comparing numeric values of paired samples, differential values for each pair of values will be computed. Then, the distribution of those differentials will be compared with the normal distribution, using the Shapiro-Wilk test. If the differentials are normally distributed, we will use a one-sample Student T test (equivalent with the Student T test for paired samples) with null hypothesis  $\mu=0$ . If the differentials are not normally distributed, we will use a Wilcoxon signed-rank test with null hypothesis location=0.

For comparing numeric values of unpaired samples the normality of the values in each sample will be tested using Shapiro-Wilk test. If values from both samples are normally distributed, then variance equality between the samples will be assessed using the Bartlett test.

If the variances are equal, then the differences between the two samples will be assessed using a Student T test for unpaired samples and equal variances. If the variances are not equal, then a Student T test for unpaired samples and unequal variances will be used. In both cases, the null hypothesis will be that mean difference is equal to 0. If values from at least one of the samples are not normally distributed, then a Wilcoxon rank sum with null hypothesis of location difference equal to 0 will be performed.

For comparing ordinal values of paired samples, a Wilcoxon signed-rank test will be used, and for unpaired samples, a Wilcoxon rank-sum test will be used.

For comparing the difference in prevalences of variants of one dichotomous or nominal variable, among the groups of another dichotomous or nominal variable (i.e. testing the association between two dichotomous/nominal variables), the Chi test will be used or, where its assumptions would be violated (mainly due to small number of patients in any group), Fisher exact test will be used.

Where applicable, the two-tail p-value is reported. The type 1 error is assumed to be  $\alpha=0.05$ , and as such, results were considered statistically significant for  $p<0.05$ .

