### Descriptive statistics

The following demographic data will be presented as part of the descriptive statistics: age at stroke onset, gender, educational level, writing hand, alcohol and other substance abuse, as well as baseline WAB and NIHSS scores. Quantitative variables will be described as mean±standard deviation, while qualitative variables will be described through absolute and relative frequencies.

Average scores for each scale at each time point and for each group will be presented in table format, as well as in boxplot graphics.

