## Comparability between study groups

Compatibility between groups will be tested for the following variables: age (at stroke onset), gender, education level, writing hand, alcohol and other substance abuse, WAB scores (and their specific subscales) and NIHSS scores.

- Dichotomous variables will be tested using Chi test or, where its assumptions are not met due to small group size, Fisher's exact test.
- Qualitative ordinal variables, such as education level or alcohol/substance abuse, will be tested using Wilcoxon rank-sum tests.
- For quantitative variables, initially, normality distribution will be assessed for each group individually using the Shapiro-Wilk test. If the values for at least one group are not normally distributed, Wilcoxon rank-sum tests will be used. If values from both groups are normally distributed, equality of variances will be assessed using Bartlett test and then a Student T test for unpaired samples and equal or unequal variances will be used.

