## Exploratory statistics

For WAB scores (and their specific subscales) as well as for NIHSS scores, we will calculate the differences between the scores at visits 2/3/4, and their corresponding baseline scores. These differences will be denoted with a lowercase letter "d." Throughout this section, we will refer to these values as *differentials*.

We will assess the normality of the differentials distributions for each group and visit using the Shapiro-Wilk test.

- If the distributions of the differentials show no statistically significant differences compared to the normal distribution, across all groups and visits, then those differentials will be tested against null hypotheses of  $\mu=0$  using one sample Student T test. This would be the equivalent of testing the values of the scores for each group, at visit 2/3/4, against the baseline measurements of each respective group using paired-sample Student T test. Moreover, for each visit, we will compare the differentials between groups using Student T test for unpaired samples and equal or unequal variances, depending on the result of a Bartlett test for variance equality between groups.
- In cases where significant differences exist in the distribution of the differential values for certain groups and visits, compared to the normal distribution, we will test all differentials against the null hypothesis of location=0 using a one-sample Wilcoxon signed-rank test. This approach is equivalent to comparing the values of the scores for each group at visits 2, 3, and 4 against their corresponding baseline measurements using a Wilcoxon signed-rank test. Moreover, for each visit, we will compare the differentials between groups using a Wilcoxon rank-sum test.

For BI and mRS scores, differences from visit 2 to visit 3 and 4 respectively will be assessed in the same way, with paired-sample tests, and differences between groups will be assessed using unpaired-samples tests. .

The number of patients with at least an active AE, SAE and specific AE class, will be reported. Incidence of AEs, SAEs and AE specific classes will be compared between groups using

Chi test or where its assumptions are violated, Fisher's exact test. Moreover, the number of AEs and SAEs for each patient will be compared between groups using Wilcoxon rank-sum tests.

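### Between-arm tests of the Barthel Index and mRS leave out baseline NIHSS, and at Visits 3 and 4 they compare change from Visit 2 instead of the scores named as the endpoint

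*SAP*

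**What the plan says.** **Endpoint.** The Efficacy part of Secondary endpoints lists "Comparison of the modified Rankin Scale (mRS) scores between the Cerebrolysin and placebo groups at each follow-up time point". The time points meant are Visits 2, 3 and 4. BI is listed in the same terms. For both scales the section adds a look at the later two visits against Visit 2.

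**No baseline for these scales.** Coding systems utilized states that only the Visit 2, 3 and 4 values of BI and mRS "are available, with no value at baseline". The Visit schedule agrees: under "Visit 1 - Day 0 - Baseline, 3-5 days post-stroke" it lists WAB and NIHSS, but neither BI nor mRS.

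**Test.** In Statistical analysis, the rule for ordinal data is that "for unpaired samples, a Wilcoxon rank-sum test will be used". Exploratory statistics adds, for BI and mRS, that "differences between groups will be assessed using unpaired-samples tests". No section names a covariate for any between-arm test.

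**Use of baseline NIHSS.** It is described ("as well as baseline WAB and NIHSS scores", Descriptive statistics), tested for balance among other variables ("WAB scores (and their specific subscales) and NIHSS scores", Comparability between study groups), and subtracted from later NIHSS values. The SAP does not say what follows if the balance test is significant.

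**Code and tables.** In the R supplement, `table_them_all` handles BI and mRS with `already_diff = F`. At Visit 2 it passes the raw scores of the two arms to `test.numeric.unpaired`. At Visits 3 and 4 it first replaces each score by its difference from the same patient's Visit 2 score. Planned tables describes the BI and mRS tables in the same way.

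**The concern.** Two things are at stake.

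First, BI and mRS cannot be corrected for their own starting value. WAB AQ and NIHSS at least have a baseline to subtract. For BI and mRS, the obvious substitute is the stroke severity score already taken at Visit 1, and the plan does not use it. If severity at entry predicts later disability, leaving it out costs precision. A chance difference in severity between arms of 60 can then imitate or mask a functional effect.

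Second, the endpoint section promises a comparison of scores at three time points, but the code and tables deliver one only at Visit 2. The first treatment cycle runs over study days 1 to 14 (Treatment schedule), so an effect may already be present at Day 30. A test of change from Day 30 removes that effect from the Day 60 and Day 90 results.

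**Working it through.** **1. The plan's own figure.** Inputs from Assumed parameters and resulted sample size: d = 0.5, alpha 0.05, beta 0.2, 1:1 allocation, Wilcoxon-Mann-Whitney, 53 per group. I use the noncentral t with n multiplied by the asymptotic relative efficiency (ARE) for a normal parent, 3/π = 0.955. One-sided 0.05 then gives exactly 53 per group (power 0.803). The two-sided test specified in Statistical analysis needs 67 by the same method. That mismatch is a separate point. Here it confirms the method and shows that two-sided power is the right reference.

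**2. Power of a score comparison, 60 per arm, two-sided 0.05.**

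- Effective n = 60 × 3/π = 57.3; df = 2 × 57.3 − 2 = 112.6.
- Noncentrality = d/√(1 − r²) × √(57.3/2) = d/√(1 − r²) × 5.352, where r is the correlation of baseline NIHSS with the outcome. The SAP gives no r, so a range is assumed.

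| r | d/√(1 − r²) | noncentrality | power |
|---|---|---|---|
| 0 (unadjusted) | 0.500 | 2.676 | 75.6% |
| 0.3 | 0.524 | 2.805 | 79.4% |
| 0.4 | 0.546 | 2.920 | 82.5% |
| 0.5 | 0.577 | 3.090 | 86.5% |
| 0.6 | 0.625 | 3.345 | 91.3% |

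In information terms, 60/(1 − r²) gives 66 patients per arm at r = 0.3 and 80 at r = 0.5.

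**3. Chance imbalance.** The difference in mean baseline NIHSS has standard error √(2/60) = 0.183 SD, so its 95% range is ±0.36 SD. At that limit an unadjusted score comparison shifts by r × 0.358, which is 0.11 SD at r = 0.3 and 0.18 SD at r = 0.5, against a planned effect of 0.5. Given an imbalance of 1.96 standard errors, the test statistic is normal with mean 1.96r and variance 1 − r². The conditional type I error is then 7.9% at r = 0.3 and 12.9% at r = 0.5. At an imbalance of one standard error it is 5.0% and 4.8%.

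**4. What the coded Visit 3 and 4 tests do.** Simulation with a seven-level ordinal outcome, 60 per arm, 3,000 runs per setting and an assumed latent between-visit correlation of 0.85. Rejection rates at Visit 4:

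| Effect (Visit 2, Visit 4) | r | scores, rank-sum | scores, rank ANCOVA on NIHSS | change from Visit 2, rank-sum |
|---|---|---|---|---|
| 0.5, 0.5 | 0.3 | 74.1% | 77.5% | 5.0% |
| 0.5, 0.5 | 0.5 | 74.7% | 84.6% | 5.3% |
| 0.25, 0.5 | 0.3 | 73.6% | 77.3% | 52.4% |
| 0.25, 0.5 | 0.5 | 75.2% | 84.3% | 53.5% |

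Under the null, across r = 0.3, 0.5 and 0.7, rejection was 4.3 to 4.9% for the unadjusted score tests, 4.8 to 5.4% for the adjusted ones and 5.0 to 5.4% for change. An effect that is steady from Day 30 is invisible to the coded Visit 4 test.

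**5. Would NIHSS help the change tests?** The correlation of NIHSS with change is (r₄ − r₂)/√(2(1 − ρ)), where ρ is the between-visit correlation. It is zero if r₂ = r₄. With assumed values r₂ = 0.5, r₄ = 0.4 and ρ = 0.8, it is −0.1/√0.4 = −0.16, and power moves only from 75.6% to 76.6%. The gains in step 2 therefore belong to score comparisons alone.

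**The case against.** The strongest reply is that the planned tests are valid. Randomisation and the simulated null rates show overall type I error near 5% without adjustment, and chance imbalance is already part of that error rate. The endpoints are secondary, the trial is exploratory, and Confirmatory statistics plans nothing. All of this stands, and it limits the weight of the point.

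The size also rests on an assumed correlation. At r = 0.3 the gain is about 4 points, and the SAP does not tie d = 0.5 to BI or mRS. That stands too, which is why a range is shown.

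A reader might infer that all six coded BI and mRS between-arm tests (two scales, three visits) lose 4 to 16 points of power for want of NIHSS. The documents do not support that. Four of the six, at Visits 3 and 4, are tests of within-patient change, in which stable severity largely cancels and adjustment would add almost nothing. Those tests can also detect an effect that emerges only after Day 30. But cancelling severity in this way also cancels any effect present at Day 30, and the score comparison that the endpoint section names is still missing.

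Finally, the simulation checked rank ANCOVA on an mRS-like scale. It did not check a proportional-odds model or BI separately.

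**Conclusion.** The point holds in two parts. No between-arm test of BI or mRS uses baseline NIHSS, although these scales have no baseline of their own and NIHSS is collected at Visit 1. And the code and planned tables do not deliver the score comparisons at Days 60 and 90 that Secondary endpoints specifies.

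For score comparisons (Visit 2 as coded, all three visits as the endpoint is worded), adjustment is worth about 4 to 16 points of power for an assumed correlation of 0.3 to 0.6. It also protects against conditional bias when severity happens to be unbalanced. The near-5% power of the change test applies when the effect is equal at Visits 2 and 4, under the simulated between-visit correlation of 0.85.

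It would be wrong to infer that the unadjusted tests inflate the overall false-positive rate. They do not. The adjustment is an inexpensive improvement in precision and should be made, but the trial's validity does not depend on it.

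**What to change.** - In Secondary endpoints (Efficacy), Exploratory statistics, Planned tables and `table_them_all`, state that the BI and mRS scores themselves are compared between arms at Visits 2, 3 and 4.
- Name baseline NIHSS as the prespecified covariate, before unblinding. Use rank ANCOVA for both scales: rank the outcome over both arms, regress it on arm and ranked `NIHSST_1`, and test the arm coefficient. A proportional-odds model is an acceptable alternative for mRS.
- Keep the unadjusted rank-sum test of the scores as a sensitivity analysis.
- If change from Visit 2 is kept, label it as a description of the course after Day 30, separate from the score comparison.

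**Cost.** SAP wording and a few lines of R, with no new data. `table_them_all` takes four columns, and the long-format rows for Visits 2 to 4 do not carry the baseline value, so `NIHSST_1` must be merged in. Rank ANCOVA runs in base R. A proportional-odds model needs a library beyond the four in Software utilized, to be justified in the CSR as that section requires. The small statistical downside is an added model assumption, which the retained rank-sum test covers.

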### Secondary objectives

The secondary objectives of the ESCAS study include the following:

- To assess the efficacy of Cerebrolysin and speech therapy versus placebo (saline solution) and speech therapy at 30, 60, and 90 days after baseline using measures of motor, neurological, and global functional outcome. These outcomes will be evaluated using the National Institutes of Health Stroke Scale (NIHSS), Barthel Index (BI), and modified Rankin Scale (mRS) scores at each time point.
- To evaluate the safety of Cerebrolysin and speech therapy versus placebo (saline solution) and speech therapy at 30, 60, and 90 days after baseline. Safety will be assessed by comparing the incidence of adverse events (AEs) and severe adverse events (SAEs) between the two treatment groups.
  - Additionally, we will measure specifically neurological, psychiatric, cardiovascular, renal, hematological, gastrointestinal, metabolic, respiratory, immune-related, ENT, ophthalmic and osteoarticular related adverse events.

The secondary outcome measures include changes in NIHSS, BI, and mRS scores from baseline to each follow-up time point (30, 60, and 90 days), as well as the incidence of AEs and SAEs.

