## Assumed parameters and resulted sample size

Using G\*Power 3.1.9.7 and assuming a medium effect size  $d=0.5$ , an alpha error of  $\alpha=0.05$  and  $\beta=0.2$ , with an allocation ratio of 1 for Wilcoxon-Mann-Whitney test between two groups, we obtained a sample size of 53 patients per group. In order to provide a margin of error for situations such as patient withdrawal, SAEs or protocol violations, we have decided to recruit 120 patients in total for our study, 60 for each arm.

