### Safety

- Incidence of AEs, SAEs and specific types of AEs. These safety endpoints will be used to evaluate the tolerability and safety profile of Cerebrolysin in the study population.

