(sum(t[2,])*sum(t[,1])/bigtotal>=5) &
(sum(t[2,])*sum(t[,2])/bigtotal>=5)
ret<-c(
"p_chi2_cor"=chisq.test(t)$p.value,
"p_chi2"=chisq.test(t,correct = F)$p.value,
"p_fisher"=f$p.value,
"p_chosen"=ifelse(can_use_chisq,chisq.test(t,correct = F)$p.value,f$p.value),
"can_use_chi2"=can_use_chisq,
"OR"=t[1,1]*t[2,2]/(t[1,2]*t[2,1]),
"OR_inf"=exp(log(t[1,1]*t[2,2]/(t[1,2]*t[2,1]))-1.96*sqrt(1/t[1,1]+1/t[1,2]+1/t[2,1]+1/t[2,2])),
"OR_sup"=exp(log(t[1,1]*t[2,2]/(t[1,2]*t[2,1]))+1.96*sqrt(1/t[1,1]+1/t[1,2]+1/t[2,1]+1/t[2,2])),
"OR_Fisher"=unname(f$estimate),
"OR_F_inf"=f$conf.int[1],
"OR_F_sup"=f$conf.int[2],

```

```

"shorthand"=paste(
  ifelse(can_use_chisq,"Chi2","Fisher")," ",
  beautiful.p.value(ifelse(can_use_chisq,chisq.test(t,correct = F)$p.value,f$p.value)),
  " OR=",
  round(t[1,1]*t[2,2]/(t[1,2]*t[2,1]),3),
  sep=""
)
)
ret
}
else
{
f<-fisher.test(t)
y<-0
for(j in 1:nrow(t))
  for(k in 1:ncol(t))
    y<-y+(sum(t[j,])*sum(t[,k])/sum(t))>=5)
can_use_chisq<-(y/(nrow(t)*ncol(t))>=0.8)
ret<-c(
  "p_chi2_cor"=chisq.test(t)$p.value,
  "p_chi2"=chisq.test(t,correct = F)$p.value,
  "p_fisher"=fisher.test(t)$p.value,
  "p_chosen"=ifelse(can_use_chisq,chisq.test(t,correct = F)$p.value,fisher.test(t)$p.value),
  "can_use_chi2"=can_use_chisq,
  "shorthand"=paste(
    ifelse(can_use_chisq,"Chi2","Fisher")," ",
    beautiful.p.value(ifelse(can_use_chisq,chisq.test(t,correct = F)$p.value,f$p.value)),
    sep=""
  )
)
ret
}
}
descr.numeric.meansd<-function(x){
  return(paste0(round(mean(x),3),"±",round(sd(x),3)))
}
descr.numeric.median<-function(x){
  x<-quantile(x)
  return(paste0(round(x[3],3)," (",round(x[2],3)," - ",round(x[4],3),")"))
}

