# AE information table -----
db_adver2<-db_assign
for(i in 1:nrow(db_adver2)){
  rdmnum<-db_adver2$RDMNUM[i]
  db_adver2[i,"AE_total"]<-sum(db_advers$RDMNUM==rdmnum)
```

```
db_adver2[i,"SAE_total"]<-sum(db_advers$RDMNUM==rdmnum&db_advers$SAE=="yes")
for(j in
c("neurological","psychiatric","cardiovascular","renal","hematological","gastrointestinal","metabol
ic","respiratory","immune.related.AE","ENT","ophthalmic","osteoarticular"))
  db_adver2[i,paste0("AE_",j)]<-
sum(db_advers$RDMNUM==rdmnum&db_advers[,paste0("is_",j)]==1)
}
tbl_out<-data.frame(
  AE_category=as.character(),
  sub=as.character(),
  Crb=as.character(),
  Plc=as.character(),
  pval=as.character(),
  test=as.character()
)
db_aelong<-data.frame(
  AE_category=as.character(),
  is_crb=as.logical(),
  no_patients=as.numeric(),
  no_aes=as.numeric(),
  percent_patients=as.numeric()
)
for(i in 7:20){
  rws<-nrow(tbl_out)
  tbl_out[rws+1,1]<-db_names[i,"short"]
  tbl_out[rws+1:5,2]<-c("Patients with AEs in group","Total number of AEs in group","Mean
number of AEs per patient","Median (Q1-Q3) number of AEs per patient","Max number of AEs
per patient")
  xc<-db_adver2[db_adver2$is_crb,db_names[i,"short"]]
  xp<-db_adver2[!db_adver2$is_crb,db_names[i,"short"]]
  tbl_out[rws+1,3]<-paste0(sum(xc!=0)," (",round(sum(xc!=0)/length(xc)*100,3),"%)")
  tbl_out[rws+1,4]<-paste0(sum(xp!=0)," (",round(sum(xp!=0)/length(xp)*100,3),"%)")
  x<-contingency.table.test(table(db_adver2$is_crb,db_adver2[,db_names[i,"short"]]!=0))
  tbl_out[rws+1,5]<-beautiful.p.value(x[["p_chosen"]])
  tbl_out[rws+1,6]<-x[["shorthand"]]
  tbl_out[rws+2,3]<-sum(xc)
  tbl_out[rws+2,4]<-sum(xp)
  tbl_out[rws+3,3]<-descr.numeric.meansd(xc)
  tbl_out[rws+3,4]<-descr.numeric.meansd(xp)
  tbl_out[rws+4,3]<-descr.numeric.median(xc)
  tbl_out[rws+4,4]<-descr.numeric.median(xp)
  tbl_out[rws+5,3]<-max(xc)
  tbl_out[rws+5,4]<-max(xp)
  x<-test.numeric.unpaired(xc,xp)
```

```

tbl_out[rws+3,5]<-beautiful.p.value(x$p.value)
tbl_out[rws+3,6]<-x$final.test
for(j in 1:max(xc, xp)){
  tbl_out[rws+5+j,2]<-paste0("Patient with ",j," AEs")
  tbl_out[rws+5+j,3]<-paste0(sum(xc==j)," (",round(sum(xc==j)/length(xc)*100,3),"%)")
  tbl_out[rws+5+j,4]<-paste0(sum(xp==j)," (",round(sum(xp==j)/length(xp)*100,3),"%)")
}
rws<-(i-7)*2
db_aelong[rws+1:2,1]<-db_names[i,"short"]
db_aelong[rws+1:2,2]<-c(T,F)
db_aelong[rws+1,3]<-sum(xc!=0)
db_aelong[rws+2,3]<-sum(xp!=0)
db_aelong[rws+1,4]<-sum(xc)
db_aelong[rws+2,4]<-sum(xp)

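### The adverse-event comparison prints p-values and a point odds ratio but no interval, although at 60 per arm a non-significant result says little when events are uncommon; the code also stops if an event class is empty

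*SAP*

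**What the plan says.** The SAP lists safety among the secondary objectives: "Safety will be assessed by comparing the incidence of adverse events (AEs) and severe adverse events (SAEs) between the two treatment groups". The Safety endpoint section adds: "These safety endpoints will be used to evaluate the tolerability and safety profile of Cerebrolysin in the study population".

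The method is in Exploratory statistics: "Incidence of AEs, SAEs and AE specific classes will be compared between groups using" a Chi2 test, or Fisher's exact test where the Chi2 assumptions fail. Per-patient event counts go to a rank-sum test. The Statistical analysis section sets the common criterion: "Where applicable, the two-tail p-value is reported", and "results were considered statistically significant for" p<0.05. No section plans a risk difference or a confidence interval for an adverse-event comparison.

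The R supplement applies the tests to 14 rows: any AE, any SAE and 12 classes. `contingency.table.test` computes Wald and exact limits for the odds ratio, the last of them being "OR_F_sup'=f$conf.int[2". The AE information table block does not use them. It writes the chosen p-value and then "tbl_out[rws+1,6]<-x[['shorthand", a string holding the test name, p and the point odds ratio. Counts and percentages per arm are also written.

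The trial size was set on efficacy (a standardised difference of 0.5): the plan is to "recruit 120 patients in total for our study, 60 for each arm".

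**The concern.** A test of equal incidence answers whether the data exclude no difference. A safety objective also needs to know how large an excess the data still allow. Where events are uncommon and arms are small, the first answer is often a non-significant p whatever the truth, and only an interval gives the second. Here the code calculates limits and then drops them.

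There is also a practical risk. Several of the 12 classes (ENT, ophthalmic and immune-related, for example) could be empty in 120 patients. The code does not handle an empty class, and the Source code section prefers that the code stay unchanged after unblinding.

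**Working it through.** **The plan's own figure.** The SAP states no power for safety. Its only sample-size figure, 53 per group, concerns efficacy. It reproduces with the asymptotic-relative-efficiency method (normal parent, 3/π) at one-sided alpha 0.05, with power 0.803. Its sidedness is a separate matter and is not used below.

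**Inputs.** From the SAP: 60 per arm, two-sided 0.05, and the coded rule (uncorrected Chi2 if all four expected counts are at least 5, otherwise Fisher). With equal arms and a minority of patients affected, the rule means Chi2 when at least 10 patients in total have the event. Assumed: the placebo incidence, because the SAP gives none.

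**Miss rate.** All 61 × 61 outcomes (a events on Cerebrolysin, b on placebo) were enumerated:

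miss = 1 − Σ Bin(a; 60, p1) · Bin(b; 60, p0) over outcomes with p<0.05.

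| Placebo incidence (assumed) | Doubling missed | Tripling missed |
|---|---|---|
| 2% | 98.9% | 94.0% |
| 5% | 86.1% | 56.2% |
| 10% | 67.4% | 19.8% |
| 15% | 48.6% | 3.8% |
| 20% | 31.6% | 0.3% |

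With 53 per arm, the 5% row becomes 89.4% and 62.8%.

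**What an interval adds.** Take 9/60 on Cerebrolysin against 3/60 on placebo.

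- Chi2 = 120 × (9×57 − 3×51)² / (60×60×12×108) = 120 × 360² / 4,665,600 = 3.33, p = 0.068.
- Odds ratio = (9×57)/(3×51) = 3.35.
- Wilson limits are 8.1% to 26.1% for 9/60 and 1.7% to 13.7% for 3/60.
- Newcombe lower limit: 10.0 − √[(15.0 − 8.1)² + (13.7 − 5.0)²] = −1.1 points.
- Newcombe upper limit: 10.0 + √[(26.1 − 15.0)² + (5.0 − 1.7)²] = +21.6 points (from unrounded limits).

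The planned table would print the counts, 15% and 5%, p = 0.068 and OR 3.35. It would not print that an excess of about 22 points remains compatible with the data.

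**Which interval.** For 10/60 against 3/60, Chi2 = 120 × (10×57 − 3×50)² / (3,600×13×107) = 4.23, p = 0.040. Neither pair of limits that the code computes agrees with that test:

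- Exact odds-ratio limits: 0.90 to 22.4 (Fisher p = 0.075).
- Wald limits: exp[ln 3.8 ± 1.96 √(1/10 + 1/3 + 1/50 + 1/57)] = 0.99 to 14.6.

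The Newcombe lower limit does agree. The Wilson lower limit for 10/60 is 9.3%, so 11.67 − √[(16.67 − 9.31)² + (13.70 − 5.00)²] = +0.3 points.

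**Sparse classes.**

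- Events in the Cerebrolysin arm only, such as 5/60 against 0/60: Fisher p = 0.057. The coded odds ratio divides by zero and prints Inf.
- No events in either arm: `table(...)` has one column. The function takes its general branch and calls `fisher.test`, which stops because it needs at least two rows and two columns. The call sits inside the loop, before `write.xlsx` and the three plots.
- If that call is repaired, `test.numeric.unpaired` fails next. Both arms are constant, so it treats them as normal and calls Bartlett's test, and the resulting NaN makes `if()` stop.
- Chance of an empty class: at an assumed 1% of patients affected, 0.99^120 = 30%; at 0.5%, 0.995^120 = 55%.

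**The case against.** The SAP is exploratory: its Confirmatory statistics section plans none. Sizing a 120-patient trial on efficacy and comparing adverse events by Chi2 or Fisher is common practice. The AE table prints events and percentages per arm, so a reader can work out an interval from it. The empty-class failure is visible rather than silent, and the Source code section allows documented adjustments. All of this stands, and it makes the matter one of reporting and code rather than of design.

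Two stronger readings are tempting.

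- A reader might infer that the SAP settles safety by p<0.05 and will take non-significance as proof of it. The document does not say so. It sets no safety decision rule, and the 0.05 level is a general convention for all its tests.
- A reader might infer that a doubling or tripling of SAEs would usually be missed whatever the rate. The SAP gives no SAE rate, and the table above shows the dependence: the pair 86% and 56% belongs to a 5% placebo incidence, while at 10% or more a tripling is usually detected.

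Nor is the lack of a non-inferiority margin a fault in a trial of this kind. Exploratory status does, however, favour estimates with intervals over p-values alone.

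**Conclusion.** The point holds as a low-cost improvement. The planned safety comparison prints a p-value and a point odds ratio without an interval, at a size where a doubling is missed 49% of the time or more for placebo incidences up to 15%, and 32% of the time at 20%. These figures rest on assumed incidences and on 60 evaluable patients per arm. A non-significant p is therefore weak evidence about safety when events are uncommon.

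The code defect needs no assumption about drug effect: one empty class is enough to stop the AE table and plots. How likely that is depends on event rates that the SAP does not give.

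**What to change.** 1. In Exploratory statistics and in the AE table, report the Cerebrolysin-minus-placebo risk difference with a 95% Newcombe interval for any AE, any SAE and each class. Make this the main safety summary and label the p-values descriptive.
2. State that p of 0.05 or more will not be described as showing no difference or safety. No margin and no rule based on the upper limit is needed.
3. If odds-ratio limits are also printed, match them to the test used: exact limits beside Fisher, and a score-type interval beside Chi2. As the 10/60 against 3/60 example shows, neither coded pair is sure to agree with the uncorrected Chi2.
4. Tabulate with both levels fixed, for example `factor(x!=0, levels=c(FALSE,TRUE))`. For a class with no events, skip the tests and report the upper limit for 0/n: for 0/60, two-sided 95%, 1 − 0.025^(1/60) = 6.0%.
5. Guard `test.numeric.unpaired` for two constant arms. Replace `1:max(xc, xp)` by `seq_len(max(xc, xp))`: when the maximum is zero, the present form runs over 1 and 0 and overwrites the row holding the maximum.

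The cost is SAP wording and a few lines of R, with no new data or patients. The downside is wide intervals, which make the safety statement look less favourable.
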